Justification to include smokeless tobacco and e-cigarette users: We will include users of smokeless tobacco or e-cigarettes given the high prevalence of e-cigarette and smokeless tobacco products among young adults (26-28). As noted above, urine cotinine will be used to biochemically confirm the subjects' nicotine consumption and smoking status and used as a covariate in all analyses if required.

Subject sampling to account for sex, race, dependence symptoms, and smoking frequency: We are planning to enroll Caucasian and African-American smokers while maintaining an approximately equal male-to-female ratio.

We will create dichotomous variables to be used as a covariate to match groups on race (European American and African American) and sex because of the potential influence of race and sex on smoking behavior and nicotine pharmacokinetics (22, 29). We will also control for differences in the frequency of smoking because it may influence the behavioral effects nicotine (30-32); a continuous variable based on the reported smoking frequency (cigs per day) will be used as a covariate in the analyses if required.

8: Recruitment:

Hundred subjects will be recruited. The goal is to have 70 completers, 35 menthol and 35 non-menthol cigarette smokers.

9. Research Plan:

A. Overview

Experimental Summary: Subjects will complete five separate experimental sessions on five separate days with each session beginning around 8 AM (Fig 2). Each session (1 to 15 days apart) will include one infusion condition that will be either saline or nicotine at four different infusion rates. The five infusion conditions will be assigned randomly to one of the five experimental sessions. All infusions will last 10 minutes and be controlled by two infusion pumps, a saline infusion pump and a nicotine infusion pump. The 0.24 mcg/kg/s condition will include a 1 minute infusion of nicotine followed by a 9 min infusion of saline; the 0.096 mcg/kg/s condition will include a 2.5 minute infusion followed by a 7.5 min infusion of saline; the 0.048 mcg/kg/s condition will include a 5 min infusion of nicotine followed by a 5 min infusion of saline; the 0.024 mcg/kg/s condition will include a 10 min infusion of nicotine and no infusion of saline; and the placebo condition will include a 10 min infusion of saline and no

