infusion of nicotine. The most rapid nicotine infusion rate, 0.24 mcg/kg/s, has proven to be well tolerated in our prior studies (12, 18-20, 22). The total weight-adjusted nicotine dose will not exceed 1.2 mg. Subjects will complete baseline assessments after an indwelling catheter is inserted into an antecubital vein for safety and drug administration. Immediately prior to the start of the infusion (@ min 0) and at intervals following the start of the infusion, heart rate, blood pressure, DEQ and withdrawal assessments will be taken as shown in **Fig 2**. At the end of the session (min 120), subjects will complete the Drug versus Money Multiple-Choice Form (\$MCP) (23).

Session procedures: Before the experimental session, subjects will be required to abstain from smoking for 10h, which will be verified by expired air CO levels \leq 10 ppm (33, 34). Subjects will also be asked to refrain from consuming alcoholic beverages and drugs prior study participation, which will be verified by urine drug screening and breathalyzer before the sessions. Subjects that are non-compliant will be rescheduled or, if they are repeatedly non-compliant, discharged from the study. Subjects will be instructed to drink their typical amount of caffeinated beverages to minimize caffeine withdrawal, which could confound the study measures. Subjects will be instructed not to eat for 4 h before the sessions to minimize heartburn or nausea that can be associated with IV nicotine administration. A light meal will be provided at the end of each session.

Fig # 2 Schedule of Events: Experimental Session*

| Time point | Measures and Events |
|------------|--|
| Baseline | CO, urine and blood samples, HR/BP, M-NWSC, BQSU, SAFTEE, CPT |
| 0 min | IV Infusion starts |
| 1 min | HR/BP, DEQ, plasma nicotine |
| 3 min | HR/BP, DEQ, plasma nicotine |
| 5 min | HR/BP, DEQ, plasma nicotine |
| 8 min | HR/BP, DEQ, plasma nicotine |
| 10 min | IV Infusion ends, plasma nicotine |
| 11 min | HR/BP, DEQ, BQSU, plasma nicotine |
| 12 min | HR/BP, plasma nicotine |
| 13 min | HR/BP, DEQ, plasma nicotine |
| 15 | HR/BP, DEQ, plasma nicotine |
| 18 | HR/BP, DEQ, plasma nicotine |
| 20 | HR/BP, DEQ, plasma nicotine |
| 25 | HR/BP, DEQ, |
| 30 min | HR/BP, DEQ, BQSU, CPT, M-NWSC |
| 40 | HR/BP, DEQ, plasma nicotine |
| 50 | HR/BP, DEQ, plasma nicotine |
| 60 | HR/BP, DEQ, BQSU, M-NWSC CPT, plasma nicotine |
| 90 | HR/BP, DEQ, BQSU, M-NWSC CPT, plasma nicotine |

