| 120 min | End of session, HR/BP, DEQ, plasma nicotine, M-NWSC, BQSU, SAFTEE, CPT |
| 180 min | Discharge |

*Saline infusions will follow each nicotine infusion to maintain a 10 min total infusion time for each experimental session. Abbreviations: CO: Alveolar carbon monoxide; HR/BP: Heart rate/Blood pressure; M-NWSC: Minnesota Nicotine Withdrawal Symptom Checklist; BQSU:

Brief Questionnaire of Smoking Urges; CPT: Continuous Performance Test; DEQ: Drug Effects Questionnaire; SAFTEE: Systematic Assessment for Treatment Emergent Events.

B. Medical Monitoring And Safety

Subjects will be given a thorough physical examination as part of the post-consent screening procedures. For nicotine administration sessions, a physician or a nurse will be present and subjects will be attached to a cardiac monitor as well as a blood pressure and heart rate monitoring device. One IV catheter will be in place in each arm or only one if two IV's can't be placed. Subjects will be administered nicotine only if the systolic blood pressure is < 150 mmHg and heart rate is < 90 beats/minute. The procedures will terminate if blood pressure at any time is >170/110 mm Hg, the heart rate is >130 beats/min, or if they develop signs and symptoms of nicotine toxicity. Subjects will remain in the laboratory for at least an hour after the experimental infusion administration. These procedures have been developed as part of our IND application for IV nicotine.

C. Measures

C.1 Intake Measures

- 1) Fagerstrom Test of Nicotine Dependence (FTND):** This self-report measure assesses the degree of nicotine dependence and has been used widely in smoking studies (Heatherton et al., 1991)
- 2) Center for Epidemiologic Studies Depression (CES-D) scale:** The CES-D is a 20-item self-report measure of depressive symptoms (35). This scale will be used at intake to control for baseline differences in depressive symptoms.
- 3) The Holmes-Rahe Life Stress Inventory (HRLSI):** This is a self-report measure of 43 common life events related with some degree of stress on an individual's life. The scale was developed by the psychologists T.J. Holmes and R. Rahe, who reported that serious physical disorders, such as myocardial infarction, peptic ulcer, infections, and a variety of psychiatric disorders were positively associated with the number of life stressors scale within a period of 1 year. This scale will be used at intake to control for baseline differences in life stress.

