- 4) PTSD Checklist for DSM-5 (PCL-5):** The PCL-5 is a 20-item self-report measure that assesses the 20 DSM-5 symptoms of PTSD(36). This scale will be used at intake to control for baseline differences in PTSD symptoms

C.2 Study outcome measures

1) Physiological:

- 1.1 Heart rate (HR) and blood pressure (BP) readings will be taken at intake during screening. During the sessions HR and BP will be monitored continuously for medical/safety reasons. The HR and BP responses will help us determine the effect of delivery rate on some of the acute cardiovascular health risks associated with nicotine (36). In our preliminary studies, the peak effect of nicotine versus saline has a large effect size. We will analyze the peak effect

(determined from assessments at min 0, 1, 2, 4, 6, 8, 10, 12, 14, 16, 18 and 20) in our primary analysis because with the peak effect we have the greatest statistical power (>0.8) to detect infusion rate differences. Additional responses will be included in secondary analyses.

2) Biochemical:

2.1 Cotinine levels: Urine cotinine levels will be determined at baseline with a semi-quantitative test strip.

2.2 Alveolar carbon monoxide: CO readings ≤ 10 ppm will be used to verify compliance with overnight smoking abstinence. In our prior work we have used plasma nicotine levels to confirm that smokers with CO ≤ 10 ppm were overnight abstinent with exceptional concordance (95% had plasma nicotine < 10 ng/ml; mean = 2.8 ng/ml (SD 3.1), N=201). The 10 ppm cutoff is higher than cutoffs recommended for distinguishing smokers from non-smokers (~ 5 ppm) but consistent, albeit slightly more conservative, than a suggested cutoff (12 ppm) for distinguishing 8 h abstinent smokers from non-abstinent smokers (25).

3) Drug reinforcement and subjective effects:

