- 3) Study procedures: On the test days, subjects will not be able to smoke for 10 hours. During this cigarette abstinence period, subjects may experience symptoms of nicotine withdrawal such as craving cigarettes, mild anxiety, restlessness, irritability, difficulty concentrating, loss of energy, and excessive hunger.
- 4) Protection of Subjects: To participate in a study, each subject must give informed consent. All potential risks will be described in detail to the subjects in the consent form. The personnel in the laboratory have been certified in either Advance Cardiac Life Support (ACLS) or Basic Life Support. If a problem arises, the subject will be treated immediately. Confidentiality in this study is of the utmost importance to us. All information obtained will be stored in coded form. The names of the subjects will be used in hospital records.

12. Safety

Prior to initiating any research activity, each subject must give informed consent. Before the study, the subjects will be informed about all potential risks of the study. Our inclusion and exclusion criteria will be applied by experienced professionals who will be carefully trained and monitored to accept only appropriate subjects into the study. Thus, effective screening will exclude subjects who would be placed at a greater risk. Eligibility is determined by the medical

and psychiatric history, drug use history, the physical examination, and the laboratory studies done prior to beginning this research protocol.

For nicotine administration sessions, a physician or a nurse will be present and subjects will be attached to a cardiac monitor as well as a blood pressure and heart rate monitoring device. An IV catheter will be in place throughout the session. Subjects will be administered nicotine only if the systolic blood pressure is <150 mmHg and heart rate is < 90 beats/minute. Subjects will be terminated from the study if the blood pressure at any time is >170/110 mm Hg, the heart rate is > 130 beats/min, or if they develop signs and symptoms compatible with nicotine toxicity. Subjects will remain in the laboratory for at least an hour after the last nicotine administration. These procedures have been developed as part of our IND for IV nicotine.

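### The pre-infusion start rule has no diastolic limit, so nicotine may be given at a diastolic pressure up to the stop threshold of 110 mmHg

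*Combined protocol and SAP*

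**What the plan says.** The start rule appears twice with the same content. Section 9.B (Medical Monitoring And Safety) reads "Subjects will be administered nicotine only if the systolic blood pressure is < 150 mmHg and heart rate is < 90 beats/minute", and Section 12 (Safety) reads "Subjects will be administered nicotine only if the systolic blood pressure is <150 mmHg and heart rate is < 90 beats/minute".

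The stop rule also appears twice, and it does carry a diastolic value. Section 9.B: "The procedures will terminate if blood pressure at any time is >170/110 mm Hg, the heart rate is >130 beats/min". Section 12 uses the same pressure limits with a heavier consequence: "Subjects will be terminated from the study if the blood pressure at any time is >170/110 mm Hg".

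The reading needed for a start check already exists. Section 9.A schedules it: "Immediately prior to the start of the infusion (@ min 0) and at intervals following the start of the infusion, heart rate, blood pressure" are recorded. Section C.2 adds that "During the sessions HR and BP will be monitored continuously for medical/safety reasons". On staffing, Section 9.B says that "a physician or a nurse will be present and subjects will be attached to a cardiac monitor".

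**The concern.** The protocol does not rely on screening alone to decide whether a subject may be dosed on a given day. It checks systolic pressure and heart rate before each nicotine infusion and sets both start limits well below the matching stop limits. It also treats diastolic 110 mmHg as serious enough to end a session. Diastolic pressure is nevertheless missing from the pre-infusion check, and nothing in the text explains why.

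Two things are at stake, both modest. The first is safety on the day. The start rule is the written control that acts before drug is given, while monitoring detects a rise only afterwards. In the fastest condition (0.24 mcg/kg/s) the whole nicotine dose is delivered in 1 minute, and the first scheduled reading is at minute 1, so a stop may come too late to limit the dose. The second is avoidable loss. Under the Section 12 wording, a subject who starts just under 110 and rises slightly leaves the study and forgoes any remaining sessions of the five. Waiting for another day might have avoided this.

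**Working it through.** **Inputs.** Start limits (Sections 9.B and 12): systolic <150 mmHg, heart rate <90 beats/min, no diastolic term. Stop limits (same sections): pressure >170/110 mmHg, heart rate >130 beats/min. The stop rule is read in the ordinary way, with either pressure value sufficient.

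**Step 1: is there a diastolic start limit elsewhere?** Section 7 requires good health and excludes medical disorders that the physician investigator considers a contraindication, but gives no blood pressure value. Section C.2 records pressure at intake without a cut-off. Sections 9.A and 11 give none. Section 12.3 lets the investigator withdraw a subject whose health may be threatened, again without a number. So there is none in these documents.

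**Step 2: margin between start and stop.** Margin = stop limit − start limit. Smallest rise to a stop = lowest whole-unit reading that triggers the stop − highest whole-unit reading that permits a start.

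| Measure | Margin | Smallest rise to a stop |
|---|---|---|
| Systolic (mmHg) | 170 − 150 = 20 | 171 − 149 = 22 |
| Heart rate (beats/min) | 130 − 90 = 40 | 131 − 89 = 42 |
| Diastolic (mmHg) | no start limit; 110 passes, so 0 | 111 − 110 = 1 |

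**Step 3: a worked case.** Take 145/108 with heart rate 85. Since 145 < 150 and 85 < 90, the start rule is met. Since 108 is not above 110, the stop rule is not. Dosing is permitted, and a rise of 111 − 108 = 3 mmHg triggers the stop.

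**Step 4: what candidate limits would give.**

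| Diastolic start limit | Smallest rise to a stop |
|---|---|
| <90 mmHg | 111 − 89 = 22 mmHg |
| <95 mmHg | 111 − 94 = 17 mmHg |
| <100 mmHg | 111 − 99 = 12 mmHg |

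**Step 5: cost of a held session (Section 16).** Travel alone is $20. If the day is paid in full, as for a session ended early on medical grounds, it is $150 + $20 = $170.

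How often a subject would present near 110, or rise past it, cannot be calculated. The documents give neither the resting diastolic distribution nor the diastolic response to nicotine.

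**The case against.** The case for leaving the rule alone is that the situation is improbable. Subjects are 18 to 35 and must be in good health. They have a full physical examination, laboratory tests and an ECG, and experienced staff apply the criteria. Section 9.A describes the fastest rate as well tolerated in earlier work, and Section 11 reports more than 100 smokers dosed intravenously without adverse events from nicotine. The start rule is a necessary condition, not a sufficient one, so whoever is present may still withhold the infusion. Both safety sections say the procedures come from the IND, which is not among these documents and may contain more. The 1 mmHg figure is the extreme corner of what is permitted, not a typical case.

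All of this stands as an argument about likelihood, and it keeps the point minor. None of it supplies a diastolic start limit. The presence of a physician or a nurse does not show who makes the dosing decision, but a written limit helps whichever of them does. If the IND already holds a limit, copying it into the protocol settles the matter.

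A reader might infer that the two rules contradict each other and that someone at, say, diastolic 115 may be dosed. The documents do not support that on the ordinary reading. The stop rule applies at any time, so a pre-infusion value above 110 already bars dosing, and the gap lies at and just below 110. Only if the stop rule required both pressures to be exceeded would the gap be wider. The text does not settle this, which is a reason to write the word or.

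**Conclusion.** The omission is real, is present in both safety sections, and is worth correcting as a low-cost safety improvement. As written, diastolic pressure has a start-to-stop margin of 0 mmHg, against 20 mmHg for systolic pressure and 40 beats/min for heart rate.

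The conclusion rests on two assumptions: that either pressure value alone triggers the stop, and that no diastolic start limit exists in a document not available here. It does not extend to a claim that subjects are likely to be dosed at such readings or harmed by it; the documents give no frequency, and the case should be rare. Nor do they require equal systolic and diastolic margins, so <90 mmHg is an example and not a derived value. Power and the planned analysis are untouched.

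**What to change.** In both Section 9.B and Section 12:

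- Add a diastolic start limit at the pre-infusion (minute 0) reading, set clearly below 110 by the physician investigators. A limit of <90 mmHg mirrors the 20 mmHg systolic margin; <95 and <100 are workable alternatives.
- Apply the start limits in all five sessions, saline included. The rule as worded covers nicotine only, and a hold confined to nicotine sessions would reveal the condition.
- If a start limit is not met, reschedule the session with its assigned condition. After repeated holds, the investigator reviews whether the subject should continue.
- Keep the stop rule in force at any time, and write it as systolic >170 or diastolic >110 mmHg. Confining it to the period after the infusion starts would relax an existing protection.

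The cost is two or three sentences per section and no new measurement. Rescheduling in Section 9.A is now written only for non-compliance, so it must be extended to vital signs. The spacing rule ("Each session (1 to 15 days apart) will include one infusion condition") usually leaves room for this, but not for a session already near day 15. Each held session adds about $20 to $170. Holds would be more frequent with <90 than with <100, which the physician investigators should weigh when choosing the limit.

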3.1 Drug versus Money Multiple-Choice Procedure (\$MCP): This procedure was developed and validated by Roland Griffiths and colleagues as an efficient tool to assess drug reinforcement in humans, including nicotine reinforcement (23, 37-39). For each experimental session (5 total), subjects will have choices between forfeiting or receiving escalating sums of money on a scale of values between -\$20.00 and \$20.00 or re-receiving that trial's infusion. The monetary scale will include values at \$0.25 increments between \$2.00 and -\$2.00 and values at \$0.50 increments from \$2.00 to \$20.00 and from -\$2.00-\$20.00. A crossover point, the value at which the subject chooses money rather than infusion, will be determined for each session.

3.2 Subjective Drug Effects: 1) Drug Effects Questionnaire (DEQ): Smokers will rate on a 100 mm scale, from "not at all" to "extremely," 12 items that are related to nicotine's effect. The items are 1) feel the "drug strength," 2) feel "good" drug effects, 3) feel "bad" drug effects, 4) like the drug effects, 5) feel high, 6) feel stimulated, 7) feel anxious, 8) feel down, 9) want more. This instrument is for a rapid detection of nicotine's effects and is adapted from a VAS (40). The DEQ will be administered at minute 0 (pre-infusion) and at minute 1, 2, 4, 6, 8, 10, 12, 14, 16, 18, 20, 30, 60, 120 post-infusion initiations. The timing of these measurements is based on our previous studies to optimally capture the physiological and subjective effects of nicotine. The peak effect of nicotine versus saline (e.g. Fig 1a, 1 minute post-infusion) has a large effect size. We will analyze the peak effect in our primary analysis because with the peak effect we have the greatest statistical power (>0.8) to detect infusion rate differences. Additional responses will be included in secondary analyses.

3.3 Cognitive Performance: CPT (Continuous Performance Test): Cognitive performance will be assessed with the continuous performance test (CPT) from the ANAM battery (University of Oklahoma): This test was chosen because of its sensitivity to tobacco withdrawal (52, 53). CPT assesses sustained attention, concentration, and working memory. For CPT, the main outcome measures will be percent correct responses and reaction time (52).

4) Withdrawal syndrome symptoms:

4.1 Minnesota Nicotine Withdrawal Symptom Checklist (M-NWSC): Smokers will be asked to rate several nicotine withdrawal symptoms on a 100 mm scale, from "not at all" to

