Positive subjective effects of nicotine will be assessed with the “Like the Drug Effects” and “Good Drug Effects” items from the DEQ, consistent with the FDA Guidance on abuse potential assessment (10). These items have been shown to correlate with the abuse potential of drugs of abuse. Effects will be tested using linear mixed effects models with peak change on each DEQ item as a response variable, cigarette-preference (menthol vs. non-menthol) as a between-subject factor, nicotine delivery condition as a within-subject factor and their interaction. Period effects will be controlled for by including test day as an additional predictor in the models. Random effects for subject and condition within subject will be used to account for correlations between repeated measures. Because of the potential skewed distributions of the subjective effects data, transformations will be applied as necessary. We will evaluate the main and interactive effects of menthol cigarette preference and delivery rate. We anticipate statistically significant main effects of menthol-preference, nicotine delivery rate and a significant interaction between menthol-preference and nicotine delivery rate. To better understand the dose effects of nicotine delivery rate and whether they are moderated by menthol preference, we will construct specific contrasts among the four doses to test whether there is an indication of significant linear, quadratic, linear on log-scale or sigmoidal dose-response relationships across, or within menthol-preference groups. The possible dose-response curves identified by the specific mean contrasts will be compared by fitting linear and non-linear (as necessary) dose-response models with continuous dose and selecting the best-fitting model by the Akaike’s Information Criterion (AIC).

To test for an effect of delivery rate on smoking urges, assessed by the BQSU (Factor 1 and 2) scores, we will use similar modeling approach described for subjective effects but we will also include time as a within-subject factor with outcomes for minute 0, 10, 30, 60 and 120. We anticipate a significant main effect of menthol-preference, nicotine delivery rate and potentially a significant interaction between menthol-preference and nicotine delivery rate.

Rationale for sample size:

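### The DEQ models analyse peak change without a pre-infusion covariate, which fixes the weight of each session's minute-0 rating at 1 and can cost precision in the delivery-rate contrasts

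*Combined protocol and SAP*

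**What the plan says.** Section 10 (Data analysis methods) specifies, for the liking and good-effects items, "linear mixed effects models with peak change on each DEQ item as a response variable". The predictors are cigarette preference, "nicotine delivery condition as a within-subject factor and their interaction". For test day the plan adds: "Period effects will be controlled for by including test day as an additional predictor in the models". The covariance is handled as follows: "Random effects for subject and condition within subject will be used to account for correlations between repeated measures". No pre-infusion DEQ rating is listed. Section 7 names other possible covariates: urine cotinine, which is to be "used as a covariate in all analyses if required", and race, sex and cigarettes per day. None is a DEQ rating.

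The reference point for the change is not stated. Three places bear on it:

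- Section 9.C.2, item 3.2, says: "The DEQ will be administered at minute 0 (pre-infusion"). The text of Section 9.A also places a DEQ immediately before the infusion.
- The Fig 2 schedule gives the Baseline row as "CO, urine and blood samples, HR/BP, M-NWSC, BQSU, SAFTEE, CPT". That row has no DEQ, and the 0 min row lists only the start of the infusion.
- Item 3.2 names the primary measure differently, without mentioning a baseline: "We will analyze the peak effect in our primary analysis because with the peak effect we have the greatest statistical power (>0.8").

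**The concern.** The natural reading of peak change is peak rating minus the same session's minute-0 rating. Subtraction gives the minute-0 rating a coefficient of exactly 1, whatever its actual relation to the later peak.

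In this crossover the rate contrasts are within-subject. Stable differences in how people use the 100 mm scale therefore cancel without any subtraction. What subtraction mainly brings into a rate contrast is session-to-session variation in the minute-0 rating. If that variation predicts the peak with a slope other than 1, some variance is left in that a covariate would remove.

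The stake is the precision of the delivery-rate contrasts and the rate-by-menthol interaction, which serve the Specific Aim and its two hypotheses.

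**Working it through.** **Plan's own figures.** The sample-size rationale in Section 10 uses a significance level of 0.025, taken here as two-sided.

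- Menthol main effect, f = 0.4 (d = 0.8): a noncentral t test with 31 per group has power 0.800, so the 31 reproduces.
- Delivery rate, f = 0.5, 56 completers (2 × 28): a noncentral F test with 3 numerator df (four nicotine rates) has power 0.796, so the 28 reproduces.
- Recruitment: 28/0.8 = 35.

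None of these uses a pre-infusion SD or correlation, so the point below does not alter them.

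**Inputs for the precision check.** Set the within-subject SD of the peak to 1. Let q be the within-subject SD of the minute-0 rating relative to it, and r their within-subject correlation across sessions. The documents give neither, so both are varied as assumptions.

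**Formulas**, as session-level variance entering a rate contrast:

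- Change score: 1 + q² − 2rq
- Weight estimated from the data (large sample): 1 − r²
- Excess: (1 + q² − 2rq) − (1 − r²) = (q − r)²
- Unadjusted peak: 1

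The excess is never negative. It is zero only when q = r, that is, when the within-subject slope r/q equals 1.

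**Variance ratio, change score to covariate adjustment:**

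| q | r = 0 | r = 0.2 | r = 0.4 |
|---|---|---|---|
| 0.25 | 1.0625/1 = 1.06 | 0.9625/0.96 = 1.00 | 0.8625/0.84 = 1.03 |
| 0.5 | 1.25/1 = 1.25 | 1.05/0.96 = 1.09 | 0.85/0.84 = 1.01 |
| 1 | 2/1 = 2.00 | 1.6/0.96 = 1.67 | 1.2/0.84 = 1.43 |

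**Simulation check.** A five-session crossover with 70 subjects gave ratios close to the formula: 1.51 against 1.54 (q = 1, r = 0.3), 1.05 against 1.04 (q = 0.5, r = 0.3) and 1.00 against 1.01 (q = 0.2, r = 0.1).

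**Translation to power, for illustration.** Suppose a single 1-df rate contrast had exactly 80% power on the change score with 56 completers. Adjustment would raise power to about:

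- 82% at q = 0.2, r = 0 (ratio 1.04)
- 86% at q = 0.5, r = 0.1 (ratio 1.16)
- 82% at q = 0.5, r = 0.3 (ratio 1.04)
- 94% at q = 1, r = 0.3 (ratio 1.54)

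**Comparison with the unadjusted peak.** The change score has the larger variance only when q² − 2rq > 0, that is, when r/q < 0.5. At q = 0.5, r = 0.3 the slope is 0.6 and the change-score variance is 0.95, below that of the raw peak.

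**The case against.** The case against has four parts.

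- **The subtraction is inferred.** No section defines the change as being from minute 0, item 3.2 speaks of a peak effect and discusses it as nicotine versus saline, and Fig 2 shows no pre-infusion DEQ. This stands. Change from minute 0 is the natural reading, but the plan has to say so.
- **The loss may be trivial.** The items ask about drug effects before any drug is given, on a scale starting at not at all. Ratings near zero, and hence a small q, are plausible. This also stands. With q at most 0.25 and r between 0 and q, the penalty is at most about 6%. Ratios of 1.43–2.00 need pre-drug ratings to vary as much as peak ratings, and nothing in the documents suggests that they do.
- **The effects are expected to be large.** The plan cites pilot nicotine effects of f > 0.6 and powers for f > 0.5. That lowers the urgency but does not make the fixed weight preferable.
- **Adjustment changes the menthol comparison.** Menthol preference is not randomised. Conditioning on each subject's mean baseline turns a difference in change into a difference at equal baseline. This stands, and the fix is limited accordingly.

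A reader might infer that subtraction adds noise to every rate contrast. That is not supported: against the raw peak it can remove variance, and at a slope of 1 it costs nothing against adjustment. A reader might also take it as given that pre-infusion ratings are only weakly related to peaks. The documents contain no data on this.

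**Conclusion.** The point holds as a modest one about efficiency. If peak change means change from minute 0, the plan fixes at 1 a weight that could be estimated from data the text says are collected. In large samples the fixed weight is never more precise for the rate contrasts or the rate-by-menthol interaction. Over r = 0 to 0.4, the variance ratio is about 1.00–1.06, 1.01–1.25 and 1.43–2.00 for q = 0.25, 0.5 and 1.

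This rests on assumed q and r, a linear relation, and the same q, r and slope in every session. If the change score is transformed for skewness, which Section 10 allows, the formula is only a guide.

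A reader might infer bias or an invalid sample size. Neither follows. The sequence of conditions is randomised, so the rate contrasts remain unbiased, and the 31, 28 and 35 per group do not depend on the pre-infusion rating. The undefined reference point and the conflict between Fig 2 and the text need correcting whatever q and r turn out to be.

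**What to change.** 1. In Section 10, define peak change as the peak rating minus the same session's minute-0 rating, and use that term in item 3.2 as well.
2. Reconcile the Fig 2 schedule with the text of Sections 9.A and 9.C.2 so that the minute-0 DEQ appears in both.
3. Keep the change score as the response in the DEQ models. Add one covariate: the session's minute-0 rating for that item minus the subject's own mean minute-0 rating over sessions. On the untransformed scale its coefficient estimates the slope minus 1, so the rate contrasts match those from modelling the peak with an estimated weight. The deviations sum to zero within each subject, so the menthol main effect remains a difference in change.
4. Treat any further adjustment of the menthol comparison for the subject-mean baseline as a separately justified sensitivity analysis, stating that its meaning differs.

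The cost is one term per DEQ model, a definition and a schedule correction. No new data are needed if the minute-0 DEQ is taken as the text describes.
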